8.1 Selection of subjects

Phase I

Around 100 staff/helpers from the district partners, COSH, HKU and other parties who will take part in the QW 2018 will be invited to participate in a brief training programme. The TTT programme will (1) provide staff/ helpers with an overview of the QW 2018 project; (2) equip them with the knowledge and new simple skills of helping smokers stop smoking in their respective communities; and (3) train them to give brief advice on smoking reduction and

use of existing SC services. The effect of the programme will be evaluated by pre- and post-tests. At least two half-day sessions of training will be held and the following topics will be covered in each session:

- (1) Introduction of COSH;
- (2) Objective and details of the QTW 2018 Campaign;
- (3) Marketing and promotion of smoke-free messages;
- (4) Global tobacco epidemic and control measures, including smoke-free policies and smoking cessation services in Hong Kong;
- (5) Smoking hazards of active smoking, second-hand and third-hand smoke;
- (6) Effectiveness of brief smoking cessation interventions and referral to and use of existing services;
- (7) Brief smoking cessation and reduction advice and counselling skills with case study and sharing; and
- (8) A brief introduction of evaluation using randomised controlled trial (RCT).

Phase II

About 70 sessions of recruitment and promotion activities will be organised with liaison with COSH aiming to recruit 1,200 participants. Well-trained smoking cessation ambassadors (about 6 per recruitment activity) will be deployed for onsite recruitment, brief intervention (e.g. brief SC advice), monitoring and evaluation. Each recruitment activity will be a study unit of the process evaluation and all the recruitment inputs and outcomes will be documented by a research staff for further analysis.

Phase III

We use the best study design possible under the constraints of the QTW to evaluate the effectiveness of new brief interventions. We follow the CONSORT (Schulz, 2010) in the design, implementation and reporting for the proposed

cluster RCT. Participants will be recruited in the community of all 18 districts during QW recruitment activities in Hong Kong.

The cluster RCT (cRCT) will have 2 arms: intervention group (Group A) and control group (Group B). The participants will be randomly assigned to one of the 2 groups based on the randomization. Individual randomization at the recruitment site can have several participants being recruited together at the same time resulting in contamination as some participants may be exposed to the unintended interventions inadvertently. Based on the method of random assignment of recruitment session, participants will be allocated according to the randomly selected session to either group. The randomization for group assignment will be generated by the investigators of the project before participant's recruitment and allocation concealment will be ensured (please refer to "Randomization" for details). The intervention study will follow the CONSORT [21] in the design, implementation and reporting for the proposed cluster RCT.

We wish to conduct individual telephone or face-to-face interviews (subject to the availability of further funding) for quitters and non-quitters participated in the RCT after completion of 6-month follow-up to explore their perceptions on the intervention, comments of improvement and factors contributing to the quitting/ non-quitting.

Inclusion criteria

- Hong Kong residents aged 18 or above
- Smoke at least 1 cigarette per day in the past 3 months
- Able to communicate in Cantonese (including reading Chinese)
- Exhaled carbon monoxide (CO) 4 ppm or above, assessed by a validated CO Smokerlyzer.

- Intent to quit / reduce smoking

Exclusion criteria

- Smokers who have communication barrier (either physically or cognitively)
- Have participation in other smoking cessation programmes or services

8.2 Procedures

Phase I: Develop a smoking cessation training curriculum for the staff from NGOs and HKU

The smoking cessation training curriculum will be designed to illustrate the psychological and behavioral therapies in managing the care of the smokers. Throughout the training, participants will be taught a variety of topics by trained nurses and trained smoking cessation counsellors including: (1) Introduction of the Quit-to-Win Contest & the RCT; (2) Smoking trend and knowledge of health hazards from smoking; (3) COSH and social marketing on smoking cessation; (4) Recruitment strategies: How to approach smokers; (5) Experience sharing in communication with smokers; (6) Assessment of quitting readiness and individualized brief counselling; and (7) Technical skills such as conducting surveys and use of Smokerlyzers and advice on smoking reduction. At the end of the program, participants should be capable of delivering brief advice of smoking cessation for smokers. Upon completion of the training program, a certificate of attendance will be awarded to each participant. The outcomes of the training will be evaluated by pre- and post-tests through a self-administered survey, which includes knowledge, attitudes, and practice of smoking cessation intervention.

Phase II: Process evaluation of the recruitment activities

Quality assurance

Throughout the process evaluation, the trained staff from HKU and NGOs will be monitored on site. Spot checks will be conducted at every venue by an

investigator or a more senior research assistant to ensure a consistent delivery of the interventions proposed. They will also be responsible to monitor the whole process of each recruitment activities, and record necessary information related to the recruitment input, outcome and other environmental factors. Recruitment input includes the number of recruitment workers, posters and leaflets used. Recruitment outcome includes the number of smokers and non-smokers approached and the number of people who pay attention to the recruitment booth. The research staff will also assess the environmental factors including weather, date, time, location, facilities that may have an impact on the achievement of the recruitment sessions.

Phase III: Recruit and provide smoking reduction/cessation counselling

At the recruitment sessions, smoking cessation counsellor will measure the potential participant's level of carbon monoxide (CO) in exhaled air, screen their eligibility for entering the contest, and provide the self-help smoking cessation booklets developed by the Hong Kong Council on Smoking and Health (COSH). Then the counsellor will explain and invite the participants to join the RCT on smoking cessation intervention. Written consent for voluntary participation in the trial will be obtained before administering the baseline questionnaire and delivery of the intervention for the participants.

Hypothesis

The major research hypothesis is: combined brief advice, personalized active-referral plus financial incentive group (Group A) will have higher validated abstinence rate than the control group (Group B). The other hypotheses include higher SC services use rate, self-reported abstinence rate, smoking reduction rate, quit attempts, intention to quit, self-efficacy of quitting in the Group A compared with Group B.

Quit to Win Contest

In the Quit to Win study, 2-arm RCT will be conducted to test the effectiveness of combined intervention of brief cessation advice, active referral and financial

incentive brief advice in achieving smoking abstinence. A detailed flow chart of the RCT is attached (Appendix 1).

Intervention Group A

Participants in Group A will receive a combined intervention:

- (1) Brief intervention using AWARD advice,
- (2) Personalized active referral to SC services,
- (3) Financial incentive for encouraging SC services use

(1) Brief intervention using AWARD model

Smokers will receive AWARD intervention delivered by the SC counsellors who completed the TTT programme and a brief warning leaflet emphasising on smoking harms (especially one out of two smokers will be killed by smoking, and the risk could be up to 2/3 for high risk smokers) and benefits of cessation.

AWARD model

AWARD will be delivered to smokers onsite and this includes: **A**sk about smoking history, **W**arn about the high risk (*with a brief health warning leaflet, see below for information*), **A**dvice to quit as soon as possible and not later than a quit date (which will qualify them for the QW prizes), **R**efer smokers to smoking cessation services (*with a referral card, see below for information*), and **D**o it again: to repeat the intervention; participants who fail to quit or relapse will be encouraged to quit again (and those who have quit will be encouraged to prevent relapse) during each telephone follow-up. The whole process of AWARD can be delivered within 30 seconds to 1 minute.

a) **Brief leaflet on health warning and smoking cessation**

The 2-side colour printed A4 leaflet, which systematically covers the most important messages to motivate SC and being used in QW 2015, will be

disseminated to smokers during the counselling, with improvements if necessary. The content of the leaflet includes: (1) highlights of the absolute risk of death due to smoking; (2) the whole list of diseases caused by active and second-hand smoking; (3) ten horrible pictorial warnings of health consequences of smoking and second-hand smoking in one page to maximize the impacts; (4) benefits of SC and (5) simple messages to encourage participants to quit smoking and remind them to call the Department of Health SC [contact].

b) Referral card

The 3-folded “Smoking Cessation Services” card which was developed and used since QTW Contest 2015 will be disseminated to smokers in this project, with improvements if necessary. The content consists of brief information and highlights of existing SC services, contact methods, motivation information and strong supporting messages or slogans.

(2) *Personalized active referral to SC services*

Similar to QTW Contests 2015, smokers in Group A will be introduced to various SC services in Hong Kong (using the referral card) and be motivated to use the services. Active referral intervention is designed to promote using the existing SC services to increase abstinence rate. Well-trained SC ambassadors will assist smoker to choose favorite/most convenient or preferred type of services: Tung Wah Group of Hospitals Integrated Smoking Cessation Centre (ISCC) services; Pok Oi Hospital Chinese Medicine smoking cessation services; Hospital Authority clinics in 18 districts; Department of Health hotline counseling; Youth Quitline; and Women Quitline. We then will send smokers’ contact details to SC services provider within 7-day and SC services providers will contact the smokers within 1-2 weeks. If the smokers are not ready to

provide personal details for booking the services onsite, we will encourage the smokers to set a day for booking within 7 days of baseline survey. SMS messages will be sent to encourage them to book the SC appointment. Research staff will monitor SC services use of the participants at each follow-up (1-, 2-, 3- and 6-month) and assist participants to book or re-book the appointments if necessary at 1- and 2- month follow-up (after very brief questionnaire surveys). We shall liaise with the existing service providers and seek their assistance in helping our smokers in a timely manner.

(3) *Incentive for promoting SC service use*

Incentive on encouragement of using SC services will be provided in intervention group (Group A) in order to motivate participants to seek existing cessation assistance. Intervention participants are informed at baseline that they will receive financial incentive (supermarket coupon HK\$300) if they attend or use any of the SC services within 3-month. Participants who are willing to book the SC services are required to sign a form stating that they are willing and will use the services. Participants who used the SC service within 3-month will receive incentive by post.

For some present-biased smokers, they pay less attention to the smoking hazards and have low levels of intrinsic motivation to quit [12]. Financial incentives have been shown to successfully promote SC, particularly among low-income smokers [22, 23]. Offering financial incentive such as cash and gift vouchers provide extrinsic motivation for smokers. Therefore, providing participants a small financial incentive for promoting SC services could be a feasible intervention to motivate more smokers to attend SC services and to increase abstinence.

Control Group: AWARD advice (Group B)

Participants in the control group will receive the AWARD advice and SC booklet as in the intervention group. Referral to SC service will be provided to participants in control group after 6-month survey.

Participants in both intervention and control groups will also receive a 12-page generic self-help SC booklet provided by COSH. It has been used since QW Contest 2013 and will be disseminated to all smokers in this project. The content includes information about benefits of quitting, smoking and diseases, methods to quit, how to handle withdrawal symptoms, declaration of quitting, etc.

Table 1. Summary of intervention in 2 groups

	Intervention (Group A)	Control (Group B)
Personalized active referral + financial incentive	✓	
Referral card + warning leaflet	✓	
AWARD advice + COSH booklet	✓	✓

Non-trial Group

Those who are unable to read or communicate using Chinese, or those who refuse to participate in the RCT, can still participate in the QW Contest and will receive the same monetary incentive if he/she passes the biochemical validations at 3- and 6- month. This group will be analysed separately from the RCT.

CSD Group

Invited by Correctional Services. Department (CSD), a group of prison smokers from Lo Wu Correctional Institution and Stanley Prison will participant the QW contest. They will not be enrolled in the RCT but they can still participate in the QW Contest and will receive the same monetary incentive if he/she

passes the biochemical validations at 3- and 6-month. This group will be analysed separately from the RCT.

Follow-up

All participants in the RCT will be followed-up at 1, 2, 3 and 6- month by telephone interview to assess their smoking status and quitting progress. At 1- and 2- month follow-up, booster interventions (see details below) will be given to participants. The follow-up at 3- and 6- month will be telephone survey only with no further intervention. Components of follow-up at 1- & 2- month in each group are:

- (1) Intervention Group A: brief AWARD intervention, enquiry and reinforce the use of SC services, assist in booking/re-booking SC services and very brief survey (only asking smoking status, abstinence, SC services use).
- (2) Control Group B: brief AWARD intervention and very brief survey.

For those unreachable participants at the schedule follow-up time, we shall make further calls, but limited to a maximum of 7 calls and 1 voice message as a reminder for their quitting. Self-reported quitters (no smoking in past 7 days) at 3- and 6- month follow-up will be invited for biochemical and non-biochemical validation. Biochemical validation includes the measurement of exhaled CO level and saliva cotinine level of the participants, which will be conducted by research assistants. The non-biochemical validation includes asking the quitter a few questions on the consequences of quitting, confirming quitter's quitting status by family members and assessment on the quitter by the interviewer. These are broadly similar to previous QW Contests.

For CSD participants, self-administered questionnaire survey will be conducted at 1- and 2- month follow-up. The follow-ups at 3- and 6-month include self-administered questionnaire survey and face-to-face biochemical validation by

research staff. Qualitative interview to CSD participants will be conducted at 6-month to evaluate the process and outcome of the program.

8.3 Randomization

By cluster randomization, all participants recruited in a particular recruitment session (one day may have more than one activities) will be allocated to one of the RCT groups. Block randomization will be used to allocate the recruitment activity into the two RCT groups to ensure the number of recruitment activities for the two RCT groups is similar. The numbers for the permutation in the blocks will be generated with the website <http://www.random.org> (a website for generating random integers), and then merge with the list of all recruitment days.

8.4 Instruments

Phase I

A course evaluation form and a self-administered questionnaire including knowledge, attitude, and practice of smoking cessation will be completed by the participants of the training workshops (Appendix 2).

Phase II

A process evaluation form will be used to record the recruitment outcomes and observations including the number of people reached in the recruitment sessions of all recruitment sessions. It will be administered by the investigators or research staff.

Phase III

Quit to Win

Three sets of questionnaires will be adapted from our previous Quit to Win Contest conducted in 2015. These include: (1) a baseline questionnaire which collects demographic data, smoking behavior, quit attempts, smoking-related psychological factors and perceived social support when they participated the Contest (Appendix 9); (2) a set of follow-up questionnaires 1 month & 2 month booster interventions (Appendix 10a-b and 11a-b); and (3) a set of follow-up

questionnaires for 3- & 6-months (Appendix 12a-b and 13a-b) which collects information on smoking behavior, quit attempts, smoking-related psychological factors and perceived social support in the quitting process, as well as the impact of the Quit to Win Contest.

8.5 Sample size

Phase I

All staff/helpers from the participated NGOs and HKU who participate in the recruitment will be invited to attend the training program. A total of 100 participants (including a minimum of 36 NGO staff and HKU student helpers) can join the smoking cessation training program.

Phase II

COSH targeted to organize at least 2 recruitment sessions in each of the 18 districts in Hong Kong. There will be about 70 recruitment sessions to be evaluated.

Phase III

Quit to Win

The computer programme G*Power is used to calculate the sample size [24]. The proposed sample size is based on the primary outcome of validated quit rate at 6-month (Group A vs. Group B). Based on our previous QW trials, the biochemically validated quit rate for the Control group was about 4.6% at 6-month follow-up [8, 12, 14]. In QW 2015 trial, 6-month biochemically validated quit rate for the moderate intensity active referral was 9.0%. Cochrane review suggested the effect size of financial interventions aimed at encouraging the use of SC treatment is 1.48 [25]. Nevertheless, we conservatively assume a smaller effect size of 1.25 for the financial incentive in a combined SC intervention. It means that the validated quit rate at 6-month for Group A and Group B will be 11% and 4.6%, respectively. To achieve 80% power with a 5% false positive error rate to detect this effect size by a chi-square test, we will

need 275 participants per group. Assuming an intra-cluster correlation coefficient as 0.015 and a retention rate of 70% at the 6-month follow-up, the overall sample size of the study should be 1134 for the 2 groups (i.e. $974 = 275 \times 2 \text{ Groups} \times 1.24 \text{ design effect} / 70\% \text{ retention rate}$).

For the post-intervention qualitative study, a purposive sample of quitter and non-quitter will be interviewed with sample size determined by data saturation.

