8.6 Statistical Analysis

Data will be entered into SPSS for Windows (version 23). A logic check program will be installed for entry validation. Descriptive statistics such as frequency, percentage, and mean will be used to summarize the outcomes and other variables. Chi-square tests and t-tests will be used to compare outcome variables between subgroups. Generalized Estimating Equation (GEE) models will be applied to test the intervention effect, to identify the baseline predictors of successful quitting and to assess the changes in smoking-related factors over time. The intention-to-treat (ITT) analysis will be used such that those lost to contact and refused cases at the follow-ups will be treated as a failure to achieve any cessation outcome. Multiple imputations will be used to compute missing data for outcome variables.

The **primary analyses** include: (1) Main effect: Intervention vs. Control on biochemically validated abstinence at 3-month and 6-month.

The **secondary analyses** include: (2) Main effect adjusting for baseline difference; (3) All secondary outcomes at 3-months and 6-months; (4) Mediation analysis of 3-month factors (psychosocial or resource effects) on biochemically validated abstinence at 6-month; (5) Subgroup analysis based on intention to quit at baseline, SC service at 3-month; (6) Cost-effectiveness

analysis over the 6-month trial period and long-term cost-effectiveness analysis over the lifetime horizon; (7) Qualitative study data analysis for understanding the effects of the intervention; (8) Network meta-analysis to combine the results of QTW 2015 and 2017 for comparing different level of active referral on quitting [26].

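### The 70% retention divisor in section 8.5 does not match the lost-as-failure rule in section 8.6, and the denominator of the assumed quit rates is not stated

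*Protocol*

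**What the plan says.** Section 8.5 (Phase III) takes the validated quit rate at 6 months as the outcome for sizing. From earlier contests it states that "the biochemically validated quit rate for the Control group was about 4.6% at 6-month follow-up". It takes 9.0% for moderate-intensity active referral from the 2015 contest and applies a multiplier of 1.25 for the incentive, concluding that "the validated quit rate at 6-month for Group A and Group B will be 11% and 4.6%, respectively". The criterion is set out as "To achieve 80% power with a 5% false positive error rate to detect this effect size by a chi-square test", which gives 275 per group. The inflation then begins "Assuming an intra-cluster correlation coefficient as 0.015 and a retention rate of 70% at the 6-month follow-up". The sentence gives an overall size of 1134, but its bracketed formula (275 × 2 groups × 1.24 design effect / 70% retention) is written as 974.

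Section 8.6 defines the intention-to-treat analysis so that "those lost to contact and refused cases at the follow-ups will be treated as a failure to achieve any cessation outcome". The next sentence adds multiple imputation for missing outcome data and does not say which of the two rules governs the primary comparison.

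Neither section says whether the 4.6% and 9.0% were calculated over everyone randomised or only over those reached at 6 months.

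**The concern.** Dividing by retention replaces participants who will drop out of the analysis. Under a lost-as-failure rule nobody drops out of it: loss to follow-up lowers the observed quit rates and leaves the denominator unchanged. The retention step in section 8.5 therefore belongs to a different analysis from the one in section 8.6.

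What follows depends on the missing denominator. If the assumed rates already count losses as failures, the division allows for loss a second time. If they are rates among those followed up, the calculation should have used diluted rates. The required size and the difference the trial was built to detect are not the same in the two cases, and a reader of the protocol cannot tell which was meant.

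**Working it through.** **Inputs.** From section 8.5: rates 11% and 4.6%, power 80%, alpha 5%, chi-square test, design effect 1.24, retention 70%, totals 974 and 1134. From section 8.1 (Phase II): target of 1,200 participants over about 70 sessions. Assumptions of this check: a two-sided test (the protocol does not state sidedness, but two-sided reproduces its figure), equal arms, and 70% retention in each arm.

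**Formula.** Pooled-variance comparison of two proportions without continuity correction, with p̄ = (p₁ + p₂)/2:

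n per group = [1.96 √(2p̄(1 − p̄)) + 0.842 √(p₁(1 − p₁) + p₂(1 − p₂))]² / (p₁ − p₂)²

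Power at a total N uses an effective size per arm of N / 2 / 1.24.

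**1. The protocol's own figures.**
- 11% vs 4.6%: n = 274.4, rounded up to 275. This reproduces.
- 275 × 2 × 1.24 / 0.70 = 974.3. The bracketed 974 reproduces.
- 1134 does not follow from that formula. It would need a design effect of 1134 × 0.70 / 550 = 1.44, or retention of 550 × 1.24 / 1134 = 60%.
- The design effect agrees with the ICC at 17 per session: 1 + (17 − 1) × 0.015 = 1.24. The target gives 1,200 / 70 = 17.1 per session.

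**2. Rates taken over all randomised.** Loss is already in the rates, so no division is needed: 275 × 2 × 1.24 = 682.

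**3. Rates taken among those followed up.** With losses scored as failures, the analysed rates are 0.70 × 11% = 7.7% and 0.70 × 4.6% = 3.22%. Then n = 402.5 per group, and 402.5 × 2 × 1.24 = 998 (999.4, so 1,000, if n is first rounded up to 403).

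**4. Power of the lost-as-failure test, everyone randomised analysed, design effect 1.24.**

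| Total N | Effective n per arm | Rates over all randomised (11% vs 4.6%) | Rates among those followed up (7.7% vs 3.22%) |
|---|---|---|---|
| 682 | 275.0 | 80.1% | 63.8% |
| 974 | 392.7 | 91.8% | 79.0% |
| 1134 | 457.3 | 95.2% | 84.8% |
| 1,200 | 483.9 | 96.1% | 86.7% |

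**5. Why the last column stays near 80% at 974.** Multiplying both rates by 0.70 raises the required n from 274.4 to 402.5, a factor of 1.47. Dividing by 0.70 raises it by 1.43. The two nearly cancel.

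**6. Sensitivity to the design effect.** If 974 people were spread over the same 70 sessions, there would be 13.9 per session and a design effect of 1 + (13.9 − 1) × 0.015 = 1.19. Power on the diluted rates would then be 80.5%.

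**The case against.** The strongest reply is that the mismatch does little harm. If the rates are completers' rates, the stated 80% is right to within about a point (79.0% with the stated design effect, 80.5% with the one implied by 974 over 70 sessions). If they are rates over all randomised, the divisor is only a conservative allowance. At 1134 or 1,200 power exceeds 80% in both cases. All of this stands.

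A reader might infer more: that the stated 80% is wrong whichever denominator was used, or that the trial is underpowered. The documents support neither inference. The first fails because of the near-cancellation in the completers' case. The second fails because the lowest power at either stated total is about 79%, and at the recruitment target it is at least 86.7%. Nor can it be asserted that loss was in fact counted twice, since that depends on earlier contest reports whose denominators the protocol does not give.

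It can also be said that section 8.6 mentions multiple imputation, under which losses are not all failures and some allowance for lost information is reasonable. That is fair, but it adds to the ambiguity: the protocol states both rules without ranking them, and the sizing does not say which one it assumes.

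What survives is narrower. The retention step and the stated missing-data rule do not belong together, and the denominator needed to reconcile them is absent.

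**Conclusion.** The point holds as a mismatch between the sizing and the planned analysis, not as a power deficit. The requirement for 80% power under the lost-as-failure rule is 682 or about 998, depending on a denominator that the protocol leaves out. The corresponding differences on the analysed scale are 6.4 and about 4.5 percentage points (11 − 4.6 and 7.7 − 3.22). The stated 80% clearly understates power only if the rates are over all randomised; otherwise it is approximately right.

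These figures rest on 70% retention in both arms, a design effect of 1.24 and a two-sided 5% test. Unequal loss between arms would change the completers' case. The change is worth making because it is cheap and because the size and power are figures on which the trial relies. It gives no reason to alter recruitment.

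**What to change.** In section 8.5, state whether the 4.6% and 9.0% are rates over all randomised or among those followed up. In section 8.6, say whether lost-as-failure or multiple imputation governs the primary analysis. If lost-as-failure is primary, then:

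- for rates over all randomised, remove the division by 70% and give the requirement as 275 × 2 × 1.24 = 682;
- for rates among those followed up, dilute them to about 7.7% and 3.2% before the calculation and give the requirement as about 998.

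If multiple imputation is primary, state the allowance made for lost information and its basis.

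In every case, reconcile 1134 with 974 and quote the power at the one total that is kept. Leave the recruitment target unchanged. In particular, do not treat 682 as a new target, because it gives only about 64% power if the rates prove to be completers' rates. The cost is a few sentences and one recalculation, with no additional participants.

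### Section 8.5 sets the trial's size at 1,134, but the equation given as its derivation yields 974; the stated 80% power belongs to 974

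*Protocol*

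**What the plan says.** The Phase III part of section 8.5 bases the sample size on the validated quit rate at 6 months. It assumes that "the validated quit rate at 6-month for Group A and Group B will be 11% and 4.6%, respectively". The design goal is worded as follows: "To achieve 80% power with a 5% false positive error rate to detect this effect size by a chi-square test". From this the protocol concludes that it will "need 275 participants per group".

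Two adjustments follow. One is for clustering by recruitment session ("Assuming an intra-cluster correlation coefficient as 0.015", with a design effect of 1.24 in the equation). The other is for 70% retention at 6 months. The conclusion is that "the overall sample size of the study should be 1134 for the 2 groups". A parenthesis in the same sentence, introduced as a restatement of that total, gives 974 as 275 × 2 groups × the design effect, divided by the retention rate.

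Elsewhere, section 8.1 (Phase II) describes about 70 recruitment and promotion sessions, "aiming to recruit 1,200 participants". Section 8.6 counts participants who are lost or who refuse follow-up as failures in the intention-to-treat analysis.

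**The concern.** One sentence gives two different totals for the same calculation. Both are legible and the equation balances at 974, so faulty text extraction or redaction does not explain the difference. No margin, rounding or further adjustment leads from 974 to 1,134.

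The total is the trial's commitment on enrolment, and the protocol undertakes to follow CONSORT in design and reporting, so the figure and its derivation will be reported. If enrolment ended between 974 and 1,134, the protocol would support both a claim that the target was met and a claim that it was missed. The sentence also attaches 80% power to a total that does not produce it.

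**Working it through.** **Inputs, all from section 8.5.** p_A = 0.11, p_B = 0.046, error rate 5%, power 80%, design effect (DE) 1.24, ICC 0.015, retention 0.70. Sidedness is not stated. I take the test as two-sided without continuity correction, because among the usual variants only that one gives 275.

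**1. Per-group size.** With p̄ = (0.11 + 0.046)/2 = 0.078 and the pooled two-proportion formula:

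n = [1.96 √(2p̄(1−p̄)) + 0.8416 √(p_A(1−p_A) + p_B(1−p_B))]² / (p_A − p_B)²

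= [1.96 × 0.3793 + 0.8416 × 0.3765]² / 0.064² = 274.4, so **275 per group**. The protocol's figure reproduces.

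**2. Total.** 275 × 2 × 1.24 / 0.70 = 682 / 0.70 = **974.3**. The printed 974 reproduces (975 rounded up, 976 for equal arms). The stated 1,134 does not: 1,134 − 974 = 160, and 160/974 = 16%.

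**3. Can another standard formula give 1,134?** The closest is the two-sided test with continuity correction, at 305 per group: 305 × 2 × 1.24 / 0.70 = 1,081. The other variants need fewer than 275 per group: one-sided 217, one-sided with continuity correction 247, unpooled 272, arcsine 264.

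**4. What would give 1,134?** Changing one input at a time:

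| Input changed | Value needed | Value stated |
|---|---|---|
| Per-group n | 1,134 × 0.70 / (2 × 1.24) = 320 | 275 |
| Design effect | 1,134 × 0.70 / 550 = 1.44 | 1.24 |
| Retention | 682 / 1,134 = 60% | 70% |

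None of the needed values is stated in the protocol.

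**5. Does the design effect explain the gap?** No. With ICC 0.015, DE 1.24 implies 17 per session: 1 + 16 × 0.015 = 1.24. That fits 1,200/70 = 17.1. At 1,134 over 70 sessions the mean is 16.2 and DE is 1 + 15.2 × 0.015 = 1.23, close to the stated value.

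**6. Power on the stated inputs.** Effective n per group = N × 0.70 / 1.24 / 2. Power = Φ{[0.064 √n − 1.96 × 0.3793] / 0.3765}.

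| Total N | Effective n per group | Power |
|---|---|---|
| 974 | 274.9 | 80.1% |
| 1,134 | 320.1 | 85.7% |

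**7. Conditional check on the 70% division.** Section 8.6 keeps lost participants in the denominator as failures, while section 8.5 inflates for their loss. The effect depends on what 4.6% and 11% count, which the protocol does not say.

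- If the rates already count lost participants as smokers, no inflation is needed. The requirement is 275 × 2 × 1.24 = 682. At 1,134 the effective n is 1,134 / 1.24 / 2 = 457 per group and power is about 95%.
- If they are rates among those followed up, the analysed rates become 0.70 × 11% = 7.7% and 0.70 × 4.6% = 3.2%. The formula in step 1 then gives 402.5 per group, and 402.5 × 2 × 1.24 = 998. Power is about 79% at 974 and about 85% at 1,134.

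**The case against.** The strongest reply is that this is a slip of wording with no harm to the trial. Much of that stands. A trial of 1,134 has about 85% to 95% power in every scenario above, and even 974 gives 79% or more. A reader might infer from two conflicting totals that the trial is underpowered. The documents do not support that: the larger figure exceeds what the stated inputs require.

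Three other inferences are tempting and also go too far.

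- **That 1,134 must come from a superseded 320 per group.** It fits (320 × 2 × 1.24 / 0.70 = 1,133.7), but so would a different design effect or retention rate. The protocol does not show which input lies behind the figure.
- **That 1,200 is a third, competing sample size for the trial.** It appears under Phase II, the process evaluation. Section 8.2 lets people who decline the trial, or who cannot read or communicate in Chinese, enter the Contest and be analysed separately. So 1,200 may include non-trial entrants, or it may be a rounded aim above the minimum. Neither contradicts section 8.5, although the relation should be stated.
- **That dividing by 70% is an error.** It is unnecessary under one reading of the rates. Under the other, the requirement moves only from 974 to about 998. Which reading is right depends on the earlier trials the protocol cites, which are not at hand.

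None of this removes the core point. The sentence still presents 1,134 and 974 as the result of one calculation, and only 974 follows from it.

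**Conclusion.** The total in section 8.5 is wrong as written. The printed equation is the correct part, and 1,134 is the figure without support. The gap is 160 participants, or about 6 percentage points of power (80% against 86%). This rests on the protocol's own rates, design effect and retention, and on a two-sided test without continuity correction, which the 275 implies. The defect is a target that cannot be traced to its inputs and a power statement attached to the wrong total; it is not a shortfall. The question of what the assumed quit rates count is minor and conditional.

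**What to change.** Keep the equation and state one consistent chain in section 8.5. Any of these would do:

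- 974 (976 for equal arms) required for 80% power, with no other total given;
- 974 required for 80% power, with planned trial enrolment of 1,134 giving about 86% on the same assumptions;
- the inputs that actually produce 1,134, with the equation rewritten to match and the power those inputs give.

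First settle whether 4.6% and 11% already count lost participants as smokers, and say so, because the totals and powers above depend on it. If they do, drop the division by 70% and restate the figures (682 for 80% power, about 95% at 1,134). If they do not, restate them as about 998 for 80% power and about 85% at 1,134.

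In section 8.1, say whether the 1,200 counts trial participants only or all Contest entrants.

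The cost is a change of wording in two sections, with no extra participants and no change to design or procedures.
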